5.5.1.2.3. Anti-HBs		
Antibodies		

Section number and Name	Description of Change	Brief Rationale
5.8.3.1. Data Reviews	Change in frequency and timing of Data Reviews.	Change in the scope of the study.
5.8.3.2. Interim Analysis	Reduction of number of planned interim analyses. They may be done instead of will be done.	Change in the scope of the study.
5.5.1.3.1. Association between Baseline Characteristics/ Viral Blood Markers and Selected Efficacy Variables	Analysis of Correlations between baseline characteristics and HBV blood markers may be done instead of will be done and at a later time point in a post hoc nature.	Clarification.
5.4.1.1.1. HBsAg Cut-offs	Number of categories reduced	Clarification.
5.4.2. Analysis Methods	Analysis of Secondary Endpoints may be done instead of will be done.	Clarification.
5.7.3. Receptor Occupancy	Section Added.	Added for completeness.

5.4.1.3. Time to Event Endpoints

5.4.2.3. Time to Event Endpoints

	Time to event endpoints have been removed.	Time to event endpoints are no longer of interest.
5.5.1.3. Time to Event Endpoints		
5.5.2.3. Time to Event Endpoints		
5.7.4. Immune Analysis	Immune Analysis may be done instead of will be done.	Clarification.
5.7.4. Viral Genome Sequence Analysis	Removed subsections. This analysis may be done instead of will be done.	Subsections were removed to simplify the analysis.
Health Economics	Section Removed.	Clarification.
HBV genotype	Section Removed.	Clarification.
Throughout the SAP	Minor grammatical, formatting, or spelling changes were made.	Typographical corrections or improved language for clarity and precision.
5.7.6. Definition of Subgroups	Removed some subgroups.	Considering the small sample size, it was

#### Statistical Analysis Plan 73763989PAHPB2008

Section number and Name	Description of Change	Brief Rationale
		decided to remove some subgroups.
6.4. Appendix 4 Protocol Deviations	List was updated to incorporate the updated list as per protocol amendment #3.	For completeness

## 1. INTRODUCTION

The statistical analysis plan (SAP) for the 73763989PAHPB2008 phase 2 trial describes the statistical analyses, and definitions to assess the efficacy, safety, tolerability, and pharmacodynamics of the combination of JNJ-73763989 (JNJ-3989), nucleos(t)ide analogs (NAs), and nivolumab in virologically suppressed, HBeAg-negative, chronic HBV-infected (CHB), adult participants < 56 years of age.

This study is part of the platform trial PLATFORMPAHPB2001 in participants with CHB. The protocol for 73763989PAHPB2008 constitutes the Intervention Specific Appendix 7 that describes all the specific and/or additional features of this study complementing the common design elements of the platform trial described in the Master Protocol.

This SAP is to be interpreted in conjunction with the clinical trial protocol amendment 1 finalized on 30 June 2022, and with the Master Protocol Amendment-3 for PLATFORMPAHPB2001 finalized on 21 January 2021.

Details on pharmacokinetic (PK) and pharmacokinetic/pharmacodynamic (PK/PD) analyses will be described in a separate analysis and modelling plan.

Objectives		Endpoints	
Pri	Primary		
•	To evaluate efficacy of the study intervention, based on HBsAg levels at FU Week 24.	•	Proportion of participants who achieve HBsAg seroclearance at FU Week 24.
Sec	ondary		
•	To characterize the safety and tolerability of the study intervention.	•	Proportion of participants who experienced AEs of interest.
		•	Safety profile of JNJ-3989 with nivolumab throughout the study (safety parameters include but are not limited to the frequency and severity of AEs and immune-related AEs, vital signs measurements, physical examinations, clinical laboratory values, and 12-lead electrocardiograms [ECGs]).
•	To evaluate efficacy in terms of changes in HBsAg levels from baseline over time during the study intervention and follow-up periods.	•	Change from baseline in HBsAg levels during the study intervention and follow-up periods. Proportion of participants with HBsAg levels below/above different cut-offs over time.
•	To evaluate efficacy in terms of HBsAg seroclearance/seroconversion during the study intervention and follow-up periods.	•	Proportion of participants with HBsAg seroclearance/seroconversion during the study intervention and follow-up periods. Time to achieve HBsAg seroclearance/ seroconversion.

# 1.1. Objectives and Endpoints

Objectives		Endpoints		
• To m du	o evaluate the efficacy as measured by blood narkers (such as HBV DNA and HBeAg) uring the study intervention and follow-up	•	Change from baseline in HBV DNA levels during the study intervention and follow-up periods.	
pe	eriod.	•	Proportion of participants with HBV DNA and HBeAg levels below/above different cut- offs over time.	
• To br	o evaluate the frequency of virologic reakthrough throughout the study.	•	Proportion of participants with virological breakthrough throughout the study.	
• To Л	o evaluate the pharmacokinetics (PK) of NJ-3989 (JNJ-3924 and JNJ-3976), and	•	PK parameters of JNJ-3989 (JNJ-3924 and JNJ-3976).	
or	ptionally of NA and/or nivolumab.	•	Optionally, PK parameters of NA and/or nivolumab.	
Explo	ratory			
To     of     qu     or	o characterize the pharmacodynamics (PD) f JNJ-3989 with nivolumab including uantification of Receptor Occupancy (RO) n peripheral T-cells.	•	Relationship of various PK parameters with selected efficacy and safety endpoints. Quantification of nivolumab RO on peripheral CD3+ T-cells by flow cytometry on whole blood.	
• To di	o explore changes in the severity of liver isease.	•	Changes in fibrosis (according to Fibroscan liver stiffness measurements) at end of study intervention (EOSI) and the end of the follow- up period versus baseline.	
• To th	o explore HBV-specific T-cell responses aroughout the study.	•	Changes from baseline in HBV-specific peripheral blood T-cell responses over time.	
• To in ho le	o explore efficacy of the study intervention a terms of changes in HBV RNA and epatitis B core-related antigen (HBcrAg) evels throughout the study.	•	Changes from baseline in HBV RNA and HBcrAg levels over time.	
• To th	o explore the HBV genome sequence aroughout the study.	•	Assessment of intervention-associated mutations over time.	
• To m	o explore medical resource utilization to nanage participants throughout the study.	•	Number and duration of medical care encounters, including surgeries, and other selected procedures (inpatient and outpatient).	
		•	Duration of hospitalization (total days length of stay, including duration by wards, e.g. intensive care unit).	
		•	Number and character of diagnostic and therapeutic tests and procedures.	
		•	Outpatient medical encounters and treatments (including physician or emergency room visits, tests and procedures, and medications).	

a Peripheral blood mononuclear cell (PBMC) samples for immune analyses will be collected at selected sites only.

## 1.2. Study Design

This is a Phase 2, open-label, 2-arm, multicenter study to assess efficacy, safety, tolerability, PK and PD of a combination of JNJ-3989, nivolumab, and NAs in virologically suppressed, HBeAgnegative, chronic HBV-infected, adult participants.

Initially a target of approximately 44 virologically suppressed, HBeAg-negative chronic HBVinfected adult participants  $\geq 18$  (or the legal age of consent in the jurisdiction in which the study is taking place) to <56 years of age were planned to be enrolled in this study.

Due to the decision to not extend further enrollment beyond the planned enrollment period and proceed with a reduced sample size, the final sample size is 37 (18 in Arm 1 and 19 in Arm 2).

This open-label study will be conducted in 3 periods:

- Screening Period (6 weeks [if necessary, e.g. for operational reasons, can be extended to a maximum of 8 weeks decided on a case-by-case basis and in agreement with the Sponsor]).
- Study intervention (24 weeks):
  - Arm 1: JNJ-3989 Q1W for the first 4 weeks and then Q4W until Week 24 + nivolumab at Week 16 + NA QD
  - Arm 2: JNJ-3989 Q1W for the first 4 weeks and then Q4W until Week 24 + nivolumab Q4W at Weeks 16, 20, 24 + NA QD
- Follow-up (FU) Period (48 weeks), during which NA treatment will be continued.

The total duration of individual participation will be up to 72 weeks (screening not included). Participants will be considered to have completed the study if they have completed all the assessments of the end of study (EOS) visit (ie, FU Week 48).

A schematic overview of the trial is presented in Figure 1.

FU: follow-up; JNJ-3989: JNJ-73763989; n: number of participants; NA: nucleos(t)ide analog; Q1W: once weekly; Q4W: every 4 weeks; QD: once daily.

Note: In red: number of participants per arm according to the initial design. In blue: the actual sample size.

At baseline, participants who meet the eligibility criteria will be randomized in a 1:1 ratio to Arm 1 or Arm 2. Randomization will be stratified by absolute HBsAg level (<100 IU/mL, 100 to <1,000 IU/mL, and  $\geq$ 1,000 IU/mL) at screening, as assessed by quantitative HBsAg assay.

If a participant prematurely discontinues treatment with JNJ-3989 before Week 24, the participant will also discontinue further treatment with nivolumab and will have an early withdrawal (WD) visit. Follow-up assessments should be obtained as per the Schedule of Activities (see Clinical Protocol Section 1.3) until 48 weeks after the end of JNJ-3989 treatment, unless the participant withdraws consent. The NA treatment will be continued until the end of the study.

If a participant prematurely discontinues nivolumab, treatment with JNJ-3989 and NA should be continued as planned, unless a treatment discontinuation rule for JNJ-3989 is also met. In that case, JNJ-3989 will also be discontinued but NA treatment should be continued as planned.

If a participant withdraws prematurely from the study, the reason for withdrawal (if known) should be documented. Participants who withdraw consent will be offered an optional safety follow-up visit to occur on the day of consent withdrawal. An internal Data Review Committee (DRC) will be commissioned for monitoring safety of participants enrolled in this study. In addition, an Independent Flare Expert Panel (IFLEP) will be appointed.

# 2. STATISTICAL HYPOTHESES

The primary hypothesis of this study is that at least one of the combination regimens of JNJ-3989+nivolumab+NA is more efficacious than JNJ-3989+NA treatment, as measured by the primary efficacy endpoint (ie, the proportion of participants with HBsAg seroclearance at FU Week 24). Because the study does not include a regimen arm without nivolumab, the hypothesis is formulated assuming a fixed response rate for JNJ-3989+NA of 1% based on previous study 73763989HPB2001 (REEF-1).

# 3. SAMPLE SIZE DETERMINATION

According to the initial protocol, a sample size of 20 participants per intervention arm which yielded  $\geq$ 85% statistical power to detect a  $\geq$ 15% and  $\geq$ 20% difference for the proportions of participants with HBsAg seroclearance at FU Week 24 in the 2 intervention arms, respectively, vs a fixed proportion of 1%. Statistical power to test the primary hypothesis was assessed for each of the intervention arms, using an exact test for a single proportion with a one-sided Type 1 error rate of 0.05 and applying the Hochberg procedure for multiple comparisons adjustment. The fixed rate assumed for the external active control (JNJ-3989 [200 mg]+NA treatment) is based on the data of study 73763989HPB2001 (REEF-1).

The total study sample size was adjusted to 44 participants (22 per arm) with 1:1 randomization ratio to each of the intervention arms, to account for an approximate 10% attrition rate.

Due to the decision to not extend further enrollment beyond the planned enrollment period and proceed with a reduced sample size, the final sample size is 37 (18 in Arm 1 and 19 in Arm 2). Under the same assumptions and methods of the initial protocol, an approximate sample size of 16 participants per intervention arm (assuming 10% attrition) yields  $\geq$ 75% statistical power to detect the same differences in HBsAg seroclearance at FU Week 24.

# 4. POPULATIONS (ANALYSIS SETS) FOR ANALYSIS

Due to a potential impact of Coronavirus Disease (COVID-19) pandemics on the study data collection, study intervention adherence and study conduct, the modified Full Analysis Set (mFAS) and modified FAS-N (mFAS-N) are defined to target the estimation of effects without the pandemic-related influences.

The primary set for efficacy analyses will be the FAS, and for the safety analyses the safety set. The FAS-N and modified FAS/FAS-N analysis sets will be used if there is a relevant difference from the FAS (>5% of participants in total). Analysis sets for analysis are described in Table 1

Analysis Sets	Description
Screened	All participants who signed the ICF for the Master
	Protocol and the ICF specific for this ISA.
Enrolled	All participants who were enrolled in this ISA.
Randomized	The randomized analysis set includes all participants
	who were randomized in the study.
Full Analysis Set (FAS)	All participants who were randomly assigned to an
	intervention arm in this ISA and received at least 1 dose
	of study intervention within this ISA. Participants will
	be analyzed according to the study intervention they
	were randomly assigned to.
Modified FAS (mFAS)	All participants who were randomly assigned to an
	intervention arm in this ISA and received at least 1 dose
	of study intervention within this ISA excluding those
	participants who, because of COVID-19 of similar
	the study prior to EU Week 24, or had no efficacy
	assessment for the primary endpoint COVID-19 or
	similar pandemics related reasons may include for
	example missed visits due to travel restriction, shortage
	of lab kits at the planned visit, missed collection of
	blood sample at key time points for the primary efficacy
	endpoint etc. Participants will be analyzed according to
	the study intervention they were randomly assigned to.
Full Analysis Set for nivolumab (FAS-N)	All participants who were randomly assigned to an
	intervention arm in this ISA and received at least 1 dose
	of nivolumab within this ISA. Participants will be
	analyzed according to the study intervention they were
	randomly assigned to.
Modified FAS-N (mFAS-N)	All participants who were randomly assigned to an
	of nivelymeth within this ISA and received at least 1 dose
	participants who because of COVID-19 or similar
	pandemics related reasons withdrew prematurely from
	the study prior to FU Week 24, or had no efficacy
	assessment for the primary endpoint. COVID-19 or

## 5. STATISTICAL ANALYSES

## 5.1. General Considerations

The SAP will use throughout the document the following definitions:

- Study agent refers to: JNJ-3989, and nivolumab
- Study intervention arm refers to:
  - Arm 1: JNJ-3989 + nivolumab (1 infusion) + NA
  - Arm 2: JNJ-3989 + nivolumab (3 infusions) + NA

## 5.1.1. Analysis Phase

The analyses phases are defined in Table 2 below.

Analysis Phase	Start Date	End Date
Screening	The date of signing the informed consent	1 day before the first study agent intake
Study Intervention	Date of first study agent intake	If participant did not withdraw from the study and did not discontinue treatment early prior to the projected/actual Week 24 Visit date: Min [Date of Week 24 study agent intake + 5 days a , cut-off date b ] Otherwise: Max [Early study withdrawal visit date, study agent discontinuation date] + 5 days a or cut-off date b , whichever occurs first
Follow-up	Participantswhodidnotwithdrawinformedconsentduringstudyinterventionphase:End ofstudyinterventionphase + 1dayOtherwise:missing	Max [study discontinuation date, study completion date] or cut-off date b , whichever occurs first

 Table 2:
 Analysis Phases Start and End Dates

a Addition of 5 days is only applicable for Adverse Events and Concomitant Medications.

Cut-off dates will be defined to match the prespecified timepoints for DRC safety monitoring, interim analyses, the primary and the final analyses, respectively.

## 5.1.2. Relative Day by Study Phase

An analysis relative day (ADY) will be calculated for all assessments at all visits for each participant by study phase.

## 5.1.2.1. Study Intervention Relative Day

Study Intervention (SI) start date (SI Day 1) is defined in Table 2. All efficacy and safety assessments during the study intervention period will be assigned an analysis day relative to this date.

The study day in the study intervention period (SI ADY) is defined as:

SI ADY = visit date - SI start date + 1

for visits on or after study intervention period Day 1, and

SI ADY = visit date - SI start date

for visits before SI Day 1 (Screening phase).

There is no 'SI Day 0'.

# 5.1.2.2. Nivolumab Relative Day

Nivolumab start date (NV Day 1) is defined as the date of the first Nivolumab administration. Efficacy and safety assessments during the study intervention (after receiving Nivolumab) and FU phase will be assigned a day relative to this date. The study day is defined as:

NV ADY = visit date - NV start date + 1

for visits on or after NV Day 1.

# 5.1.2.3. Follow Up Relative Day

Follow-up (FU) start date (FU Day 1) is defined in Table 2. Efficacy and safety assessments during the FU phase will be assigned a day relative to this date. The FU study day in the FU phase (ADY) is defined as:

FU ADY = visit date - FU start date + 1

for visits on or after FU Day 1.

## 5.1.3. Visit Windows

As participants do not always adhere to the protocol visit schedule, the following rules are applied to assign actual visits to analysis visits. All visits for all assessments (safety, efficacy or PK) will be uniquely allocated within each phase to an analysis time point based on the analysis relative day (ADY) compared with the target day based on Table 3. All assignments will be made in chronological order. Once a visit date is assigned to a visit window, it will no longer be used for a

later time point except for the end of study intervention period (EOSI) and end of study (EOS) visits. If a participant has 2 or more actual visits in 1 visit window, the visit closest to the target day will be used as the protocol visit for that visit window. The other additional visit(s) will not be used in the summaries or analyses, but they can be used for determination of clinically important endpoints. If 2 actual visits are equidistant from the target day within a visit window, the later visit is used. If there are two or more measurements on the same day, then the last measurement in chronological order will be used. If the time of the assessment is not available, the highest record/sequence number will be selected.

The listings and spaghetti plots will include all measurements, also those multiple assessments with the same visit window/phase.

End of study intervention (EOSI) and end of study (EOS) time points will be included in all analyses over time unless otherwise stated.

Table 3 provides the analysis time points and time intervals for each visit per analysis phase.

An alarsia mbaaa	Toward Dav	Analysis time point	Analysis time point	Time interval
Analysis phase	Target Day	(week)	(label)	(days)
Screening	-∞-	-1	Screening	<0
Study	1	0	Baseline	Pre-dose: 1
Intervention				
period				
	8	1	Week 1	[2, 11]
	15	2	Week 2	[12, 18]
	22	3	Week 3	[19, 25]
	29	4	Week 4	[26, 43]
	57	8	Week 8	[44, 71]
	85	12	Week 12	[72, 99]
	113	16	Week 16	[100, 127]
	141	20	Week 20	[128, 155]
	169	24	Week 24	[156, 183]
	Last visit in study	25ª	EOSI a	
	intervention period			
Follow-up	29	28	Follow-up Week 4	[1, 43]
	57	32	Follow-up Week 8	[44, 71]
	85	36	Follow-up Week 12	[72, 99]
	113	40	Follow-up Week 16	[100, 127]
	141	44	Follow-up Week 20	[128, 155]
	169	48	Follow-up Week 24	[156, 197]
	225	56	Follow-up Week 32	[198, 253]
	281	64	Follow-up Week 40	[254, 309]
	337	72	Follow-up Week 48	[310, +∞]
	Last visit in the	999 b	EOS b	
	study			

Table 3:Visit Windows

a End of study intervention (EOSI) visit will be the last post-baseline visit in study intervention period.

b End of study (EOS) visit (last available data during the follow-up visit) will be the last visit in the study.

# 5.1.4. Baseline

In general, the baseline assessment is defined as the last observed non-missing measurement before the date and time of the first administration of any of study agents.

In case the first administration measurement time is missing, the first observed measurement on SI Day 1 will be used as the baseline measurement. If no observed measurement on Day 1, the last observed measurement before Day 1 will be used as the baseline assessment.

# 5.1.5. Analysis Specifications

In general, continuous variables will be summarized using descriptive statistics including the number of participants, mean, standard error (SE), standard deviation (SD), two-sided 90% confidence interval (CI), median, and range. The 90% CI for continuous endpoints is constructed using the t-distribution. Binary or categorical variables will be summarized using the number and percentage of participants in each category and 90% CI using Clopper-Pearson exact method for the simple sample proportion (Newcombe RG,1998). For time-to-event variables, using the Kaplan-Meier approach, a summary table including number of participants included in the analysis, number of participants censored, 25th and 75th percentiles, median time-to-event and 90% CI will be shown. Graphic displays will also be used to summarize the data.

# 5.1.6. Additional Reference Timepoints

Three additional Reference Timepoints (RT) will be used for additional analyses of selected efficacy endpoints.

# 5.1.6.1. Nivo RT

The Nivo RT is defined as the last observed non-missing measurement before the date and time of the first Nivolumab administration. In case the first administration measurement time is missing, the first observed measurement on NV Day 1 (Nivolumab relative day 1) will be used as the nivolumab reference measurement. If no observed measurement on NV Day 1, the last observed measurement before NV Day 1 will be used as the nivolumab reference assessment.

The Nivo RT will be used for additional analyses for selected efficacy endpoints after Week 16 of study intervention period and FU phase.

# 5.1.6.2. W24 RT

The W24 RT is defined as the last observed non-missing measurement at the time of stopping JNJ-3989 administration at Week 24. This RT will be used for additional analyses for selected efficacy endpoints for FU phase.

# 5.1.6.3. FUW4 RT

The Follow up Week 4 RT (FUW4 RT) is defined as the last observed non-missing measurement at the FU Week 4 visit (4 weeks after the last JNJ-3989 administration). In case the measurement is missing at FU Week 4, the first non-missing measurement after FU Week 4 will be used as FU Week 4 reference assessment.

The FUW4 RT will be used for additional analyses for selected efficacy endpoints during FU phase.

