| Efficacy Evaluations  |                              |                |          |                |                |           |           |           |                          |
| Fibroscan t   |                              |                |          |                |                | X         |           |           | X                        |
| HBV Virology  |                              |                |          |                |                |           |           |           |                          |
| Blood sampling for HBV DNA   | X                            | X              | X        | X              | X              | X         | X         | X         | X                        |
| Blood sampling for HBV RNA u  |                              |                | X        |                |                | X         |           |           | X                        |
| HBV Serology  |                              |                |          |                |                |           |           |           |                          |
| Blood sampling for:  |                              |                |          |                |                |           |           |           |                          |
| Anti-HBs and anti-HBe  |                              |                |          |                |                | X         |           |           | X                        |
| HBsAg (quantitative)   |                              | X              | X        | X              | X              | X         | X         | X         | X                        |
| HBeAg (quantitative)   |                              |                | X        |                |                | X         |           |           | X                        |
| HBcrAg u  |                              |                | X        |                |                | X         |           |           | X                        |
| Exploratory serology v  |                              |                | X        |                |                | X         |           |           | X                        |

| Study Period   | Follow-up a,b,c,d |          |          |           |           |           |           |           |                          |

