## 10.10. Appendix 10: Protocol Amendment History

### Amendment 2 (28 March 2023)

**Overall Rationale for the Amendment:** The main reason for the protocol amendment is that due to difficult recruitment a strategic decision was taken to not extend further enrollment beyond the planned enrollment period and continue the study with a reduced sample size. There is no change in the benefit/risk for the participants.

| Section number and Name   | Description of Change   | Brief Rationale   |
|---|---|---|
| 1.1. Synopsis
1.2. Schema
4.1. Overall Design
9.2. Sample Size Determination   | Reduction of sample size.   | Due to difficult recruitment.   |
| 1.1. Synopsis
9.5. Interim Analysis  | Reduction of number of planned interim analyses.  | The remaining optional interim analyses at Week 24 and FU Week 12, in addition to the final analysis (at FU Week 48), provide sufficient information to assess safety and evaluate the time course of different safety and efficacy markers during study conduct. |
| 1.3.1. Schedule of Activities – Screening Phase and Study Intervention Phase
1.3.2. Schedule of Activities – Follow-up Phase
8.7. Exploratory Host Biomarkers | Removed the sentence: ‘For participants’ convenience, the coagulation test may be collected at the visit preceding the scheduled FNA biopsy.’   | Correction.   |
| 1.3.2. Schedule of Activities – Follow-up Phase
8. STUDY ASSESSMENTS AND PROCEDURES  | Reduction of samples collection and analyses during the follow-up period. Therefore, the total blood volume was updated accordingly.  | Protocol simplification without impacting participant’s safety and maintaining scientific value.  |
| 1.1. Synopsis
6.1. Study Intervention(s) Administered
6.8. Treatment of Overdose  | Added flexibility for nivolumab dosing and updated the overdose definition.   | To consider the necessary rounding and standard practice for the preparation and intravenous administration of drugs dosed by weight.   |
| 2.3.2.1. Known Risks  | Added: ‘Treatment with anti-PD-1 medications is associated with a risk of HBV reactivation in CHB patients. This risk is reduced with concurrent NA treatment or continuation of ongoing NA treatment.’ | Clarification.  |
| 2.3.3. Benefit-Risk Assessment for Study Participation  | Added: ‘Participants will be regularly monitored for HBV reactivation and virologic breakthroughs throughout the study.’  | Clarification.  |

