#### **VERSION HISTORY**

Document History	
Document	Date
Original SAP	20 September 2022
Amendment 1	23 August 2023
Amendment 2	10 June 2024

Amendment 2 (10 June 2024)

The main purpose of this SAP amendment is to document changes in the scope of the final analyses, based on results of the primary analysis.

Section number and Name	Description of Change	Brief Rationale
5.3.6. Comparisons Between Arm 1, 2 and Model-Based Virtual Nivolumab-Free JNJ- 3989+NA Regimen Control	Section Removed.	Virtual Control analysis is no longer of interest.
5.4.1.2. Continuous Endpoints	Section Updated.	Change from baseline value to the nadir is of interest only in HBsAg.
5.4.2.1.1. HBsAg Cut-offs and 5.4.2.1.4. HBeAg Cut- offs	Section Removed.	Cross-Tabulation for Quantitative Result vs. Qualitative Result Over Time for HBsAg and HBeAg removed as according to the protocol, qualitative HBsAg and HBeAg are only collected at screening and baseline.
5.4.2.2.1. HBsAg, HBeAg, HBV DNA and ALT	Section Updated.	
 
Waterfall plots of changes from Reference Timepoints in HBsAg removed
 
Descriptive statistics of changes from RTs in ALT removed
 
Changes from baseline analyses are removed for HBV DNA
 
Changes from baseline outputs are only displayed in the log 10 scale for all viral parameters
 
Change from Nivolumab RT and Follow-up Week 4 RT are of interest only for HBsAg
 

Section number and Name	Description of Change	Brief Rationale
5.5.1.3. and 5.5.2.3. Endpoints for Correlation	Section Removed.	Endpoints for Correlation is no longer of interest.
5.5.2.2.2. HBV RNA and HBcrAg	Section Removed.	Change from baseline value to the nadir is of interest only in HBsAg.
5.3.5. Subgroup Analyses of Primary Efficacy Endpoint and 5.7.6. Definition of Subgroups	Section Removed.	Subgroup Analysis is removed due to low number of observed events of interest.

## Amendment 1

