# 5.4.1. Definitions

# 5.4.1.1. Binary Endpoints

# 5.4.1.1.1. HBsAg Cut-offs

The cut-offs for HBsAg level are as follows (yes vs no):

- <1000 IU/mL
- <100 IU/mL
- <10 IU/mL
- <1 IU/mL
- <LLOQ (0.05 IU/mL)

The cut-offs for HBsAg change from baseline and Nivo RT are as follows (yes vs no):

- decrease by  $\geq 0.5 \log_{10} IU/mL$
- decrease by  $\geq 1 \log_{10} IU/mL$
- decrease by  $\geq 2 \log_{10} IU/mL$
- decrease by  $\geq 3 \log_{10} IU/mL$
- decrease by  $\geq 4 \log_{10} IU/mL$

The cut-offs for HBsAg change from FUW4 RT are as follows (yes vs no):

- increase by  $\leq 0.2 \log_{10} IU/mL$
- increase by  $\leq 0.5 \log_{10} IU/mL$
- increase by  $\leq 1 \log_{10} IU/mL$
- decrease by  $> 0.2 \log_{10} IU/mL$
- within +/- 0.2 log10 IU/mL

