# 5.4.1.2. Continuous Endpoints

# 5.4.1.2.1. HBsAg, HBeAg, HBV DNA and ALT

Actual values (original unit and/or log10 transformed values), changes from baseline (log10 transformed values) and change from RTs over time in HBsAg will be evaluated, and actual values (original unit and/or log10 transformed values), over time in HBeAg, HBV DNA and ALT will be evaluated.

Change from baseline is defined as the value at a given time point minus baseline value.

The change from baseline value to the nadir (i.e. maximum decrease for each participant) in HBsAg will be evaluated at 3 intervals: during study intervention nadir (first 24 weeks), during follow-up nadir, and entire study nadir.

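### The SAP's FU Week 4 reference for HBsAg has no scheduled HBsAg sample behind it, so on schedule the FU Week 8 value is used under a FU Week 4 label

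*SAP*

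**What the plan says.** SAP 5.1.6 introduces the extra reference points: "Three additional Reference Timepoints (RT) will be used for additional analyses of selected efficacy endpoints". The third, the FUW4 RT in 5.1.6.3, is "the last observed non-missing measurement at the FU Week 4 visit (4 weeks after the last JNJ-3989 administration". If that value is missing, "the first non-missing measurement after FU Week 4 will be used as FU Week 4 reference assessment". No latest permitted visit is given for the substitute.

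SAP Amendment 2 (Version History) narrows the use of this reference: "Change from Nivolumab RT and Follow-up Week 4 RT are of interest only for HBsAg". Two sets of results use it:

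- SAP 5.4.1.1.1: "The cut-offs for HBsAg change from FUW4 RT are as follows (yes vs no", followed by five categories in log10 IU/mL: increase of at most 0.2, at most 0.5 and at most 1; decrease of more than 0.2; and within 0.2 either way.
- SAP 5.4.1.2.1: "change from RTs over time in HBsAg will be evaluated". SAP 5.4.2.2.1 adds summaries by arm.

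In the follow-up schedule (Protocol 1.3.2), the row "HBsAg (quantitative" is blank at FU W4 and marked at the eight later visits, from FU W8 to FU W48.

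**The concern.** The reference is kept for one marker only, and that marker is not scheduled at the visit that defines the reference. A rule written for an occasional missing value then becomes the rule for every participant sampled on schedule.

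A reader of the change-from-FUW4 tables would take them as change since 4 weeks off JNJ-3989, when on schedule they show change since about 8 weeks off. Protocol 4.3 gives a reason not to treat the two as equivalent: in the earlier study with three injections every 4 weeks, mean HBsAg reached its nadir 8 weeks after the last injection. If that carries over to this regimen, which is an assumption, an 8-week reference sits at the nadir and a 4-week reference before it.

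The sponsor has already amended the SAP for a similar reason. SAP Amendment 2 dropped the cross-tabulation of quantitative against qualitative results because qualitative HBsAg and HBeAg are collected only at screening and baseline. The FUW4 RT was kept.

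**Working it through.** No sample size, alpha or power figure is involved. The check sets the schedule against the SAP rule and its visit windows.

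**1. First scheduled follow-up HBsAg (Protocol 1.3.2).**

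| Row | FU W4 | FU W8 | FU W12 to FU W48 (7 visits) |
|---|---|---|---|
| HBV DNA | X | X | X at all 7 |
| HBsAg, quantitative | blank | X | X at all 7 |

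HBV DNA has 9 of 9 visits and HBsAg 8 of 9. Both rows have nine cells, so an X lost in conversion is unlikely. Qualitative HBsAg is scheduled only at screening and baseline (Protocol 1.3.1) and cannot fill the gap.

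**2. Can visit windowing supply a FU Week 4 value?** SAP Table 3 gives FU Week 4 = days 1 to 43 and FU Week 8 = days 44 to 71. The FU W8 visit is on day 57 ± 4. With SAP follow-up Day 1 set 0, 1 or 6 days after the Week 24 date, it falls on:

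- offset 0: days 53 to 61
- offset 1: days 52 to 60
- offset 6: days 47 to 55

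All three ranges lie inside 44 to 71 and none reaches 43 or earlier. Windowing cannot rescue the definition.

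**3. Timing of the reference.** For laboratory data, SAP Table 2 starts follow-up the day after the Week 24 dose, because the 5-day extension applies only to adverse events and concomitant medications. The labelled reference, day 29, is then 29/7 = 4.1 weeks after the last dose. The reference obtained on schedule, day 57, is 57/7 = 8.1 weeks. The gap is 57 − 29 = 28 days. Counting the Week 24 visit itself as Day 1 gives (57 − 1)/7 = 8.0 weeks, or 7.4 to 8.6 with the ± 4 days.

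**4. Consequence at FU Week 8.** The reference and the FU Week 8 value are the same measurement, so the change is 0:

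| Cut-off (log10 IU/mL) | Result at change = 0 |
|---|---|
| increase ≤ 0.2 | met |
| increase ≤ 0.5 | met |
| increase ≤ 1 | met |
| decrease > 0.2 | cannot be met |
| within ± 0.2 | met |

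Of the 8 scheduled HBsAg follow-up visits, 8 − 1 = 7 carry information. If all 37 participants were on the fallback, the FU Week 8 row would read 100% for four cut-offs and 0% for the fifth in both arms.

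**5. Consequence at later visits.** Let r be the true change from FU Week 4 to FU Week 8. Change from FU Week 8 = change from FU Week 4 − r. The documents give no value for r. Over an assumed range of −0.2 to +0.5 log10, later changes are shifted by +0.2 to −0.5, the same order as the 0.2 and 0.5 cut-offs.

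**6. Could true FU Week 4 values exist?** Protocol 10.10 records under Amendment 2 (28 March 2023): "Reduction of samples collection and analyses during the follow-up period". It does not name the samples, so FU W4 HBsAg may or may not have been among them. Taking the amendment date as the switch, 28 March 2023 minus 29 days gives a Week 24 dose on 27 February 2023; minus a further 168 days gives a first dose on 12 September 2022. Only participants first dosed by about then could have reached FU Week 4 before the amendment date. First-dose dates are not given.

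**The case against.** The strongest reply is that the SAP foresaw a missing FU Week 4 value and named the substitute. The analysis is therefore defined and reproducible, and a footnote with counts by actual reference visit would cure the labelling. That would help. It would still leave a defined reference that the schedule does not collect, an uninformative FU Week 8 row and a substitute with no time limit.

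Several limits stand:

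- The number on the fallback is unknown, so 37 of 37 is an extreme case.
- The September 2022 date is not a firm bound, because site implementation dates of Amendment 2 are not given. Unscheduled samples are also possible.
- The earlier study had no weekly loading doses and no nivolumab, and a curve can be flat near its nadir. The size of the week 4 to week 8 change is not established.
- Any reference compared with itself gives zero. Counting zero as an increase of at most 0.2 is the natural reading but is not stated.
- The 8.1 weeks applies to participants dosed at Week 24. After early discontinuation the interval since the last dose can be longer.
- SAP section 1 says the plan is read with protocol Amendment 1, but the Version History says SAP Amendment 1 was aligned with protocol Amendment 2. The version wording is weak evidence either way.
- SAP Amendment 2 was written after the primary analysis, so a change of reference now is post hoc.

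None of these supplies a scheduled HBsAg sample at FU Week 4.

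**Conclusion.** The concern holds. Followed as written, the rule gives a mislabelled result for every participant sampled only on schedule: a reference at about 8 weeks reported as one at 4 weeks, with the FU Week 8 change fixed at zero. If some participants do have HBsAg values in follow-up days 1 to 43, the fault becomes a mixture of 4-week and 8-week references under one label.

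The schedule mismatch and the arithmetic at FU Week 8 are certain from the documents. The number affected, the size of the week 4 to week 8 change and the relevance of the earlier nadir are not. The scope is confined to additional HBsAg analyses, and the HBsAg cut-offs are not among the binary endpoints given confidence intervals in SAP 5.4.2.1. This should be corrected, but it does not threaten the main conclusion of the trial.

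**What to change.** In SAP 5.1.6.3, 5.4.1.1.1 and 5.4.2.2.1, replace the FUW4 RT by an FUW8 RT: for all participants, the HBsAg value in the FU Week 8 window (follow-up days 44 to 71), closest to day 57 under the existing rule in 5.1.3. Then:

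- do not substitute a later value, and report how many participants have none;
- relabel the outputs and start the change-from-reference and cut-off summaries at FU Week 12;
- report the actual reference day, and list any FU Week 4 HBsAg values that were collected;
- leave the W24 RT as the separate analysis it already is;
- record the date and reason of the change, since it follows the primary analysis.

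The cost is SAP wording, table labels and the matching derivation; no new sampling. The downside is one fewer post-reference visit (FU Week 8), and any true FU Week 4 values are listed but not used as the reference.
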